12.2 Replacement of Subjects

Subjects who withdraw from the study will not be replaced.

13 PROTOCOL VIOLATIONS

A protocol violation occurs when the subject or investigator fails to adhere to significant protocol requirements affecting the inclusion, exclusion, subject safety and primary endpoint criteria. Protocol violations for this study include, but are not limited to, the following:

- Failure to meet inclusion/exclusion criteria
- Use of a prohibited concomitant medication

Failure to comply with Good Clinical Practice (GCP) guidelines will also result in a protocol violation. The PI will determine if a protocol violation will result in withdrawal of a subject.

When a protocol violation occurs, it will be discussed with the investigator and a Protocol Violation Form detailing the violation will be generated. This form will be signed by the PI. A copy of the form will be filed in the site's regulatory binder.

14 STATISTICAL METHODS AND CONSIDERATIONS

Prior to the analysis of the final study data, a detailed Statistical Analysis Plan (SAP) will be written describing all analyses that will be performed. The SAP will contain any modifications to the analysis plan described below.

14.1 Data Sets Analyzed

All eligible patients who are randomized into the study and receive at least one dose of the study drug (the Safety Population) will be included in the safety analysis.

Completer analysis will be the data collected for all of the completers (N=100 expected).

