9.1.7 Adverse Events

Information regarding occurrence of adverse events will be captured throughout the study. Duration (start and stop dates and times), severity/grade, outcome, treatment and relation to study drug will be recorded on the case report form (CRF).

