11.2.1 Serious Adverse Experience Reporting

Study sites will document all SAEs that occur (whether or not related to study drug) per UCSF CHR Guidelines. The collection period for all SAEs will begin after informed consent is obtained and end after procedures for the final study visit have been completed.

In accordance with the standard operating procedures and policies of the local Institutional Review Board (IRB)/Independent Ethics Committee (IEC), the site investigator will report SAEs to the IRB/IEC.

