14.4 Analysis of Secondary Endpoints

First, general linear model analyses (SAS PROC GLM) will be conducted to independently examine the impact of Condition and Pain Catastrophizing (PCS) on discounting rate (k). Then, a single GLM analysis will be conducted that includes Condition, PCS, and the Condition–by-PCS interaction. A significant interaction will indicate effect modification. We will also examine the effect of biological sex on discounting, opioid withdrawal, pain VAS, and pain catastrophizing. Based on prior research, we expect females to have higher PCS scores. We will also explore how the type of chronic pain (musculoskeletal, neuropathic, mixed/other) will effect discounting. We will also explore associations between somatization (SCL-90), depression (PHQ-9) and anxiety (GAD-7) and discounting. ng.

Safety and tolerability data will be summarized by study medication.

Adverse event rates will be coded by body system and MedDra classification term. Adverse events will be tabulated by study medication and will include the number of patients for whom the event occurred, the rate of occurrence, and the severity and relationship to study drug.

Version #: 1.9 Version Date: 12/09/2020 Page 25 of 37

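### Read literally, the Safety Population leaves out anyone dosed in breach of the entry criteria; deleting the word 'eligible' closes the gap at no cost

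*Combined protocol and SAP*

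**What the plan says.** Section 14.1 defines two analysis sets. The first, the Safety Population, is "All eligible patients who are randomized into the study and receive at least one dose of the study drug". The second is for completers: "Completer analysis will be the data collected for all of the completers (N=100 expected"). There is no set of all treated participants.

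Section 13 names, among the protocol violations, "Failure to meet inclusion/exclusion criteria". On what follows from a violation it says: "The PI will determine if a protocol violation will result in withdrawal of a subject".

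Data collection carries no eligibility limit. Section 9.1.7 states: "Information regarding occurrence of adverse events will be captured throughout the study". Section 11.1 has the investigator ask about adverse events at each visit. Section 11.2.1 states: "Study sites will document all SAEs that occur (whether or not related to study drug"), from consent to the end of the final visit, with reporting to the IRB.

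For the analysis, Section 14.4 says: "Adverse events will be tabulated by study medication and will include the number of patients for whom the event occurred". It does not name the population.

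**The concern.** A safety set normally contains everyone exposed to study treatment, because the question is what happened to the people who were dosed. Adding eligibility as a condition allows a dosed person to fall outside the set.

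The people concerned are not a neutral subgroup. Several exclusion criteria in Section 6.3 are there for safety: unstable medical illness that precipitated withdrawal might affect, unstable psychiatric illness, pregnancy or lactation, and known naloxone allergy. Someone dosed despite one of these is a person in whom the protocol itself expects more risk. If that person had an event and was left out of the tables, the reported rates would be too low. In a single-site Phase 1 study of this size, one such event could be the only one of its kind.

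**Working it through.** The plan states no figure on this point, so there is none to reproduce. The check is mainly one of wording, followed by an illustration of scale.

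**Wording**

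1. Section 14.1 lists three conditions: eligible, randomized, dosed. As randomization and dosing are named separately, the first word either adds a filter or does nothing.
2. Section 13 treats a breach of the entry criteria as a violation that may or may not lead to withdrawal. A participant can therefore be ineligible and dosed, and can remain in the study.
3. Section 14.4 names no population for the adverse event tables, so the definition in Section 14.1 governs. The completer set does not fill the gap, because it is not defined for safety and omits anyone who stops after one session.
4. Section 14.1 does not say at what time point or on which criteria eligibility is judged. The criteria are themselves not fully consistent: Section 6.2 requires a urine screen negative for drugs of abuse, while Section 9.2.2 says current illicit use does not exclude. Those two passages must be reconciled. A safety set based on dosing alone would not depend on the outcome.

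**Scale**

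Inputs: planned enrolment of 130 (synopsis and Section 6.1); assumed drop-out of 25% and about 100 completers of both sessions (synopsis). As a check, 130 × 0.75 = 97.5, in line with the rounded 100. The number who receive at least one injection is not stated. Randomization closes the screening visit (Section 10.1), so some randomized participants may never be dosed. I assume 100 to 130 dosed.

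- Share of one participant: 1/130 = 0.77% and 1/100 = 1.0%.

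Now suppose that one dosed participant is ineligible and has the only event of its type (exact 95% limits; with no events in n, the upper limit is 1 − 0.025^(1/n)):

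| Assumed dosed | All dosed | Eligible only |
|---|---|---|
| 130 | 1/130 = 0.77% (0.02% to 4.21%) | 0/129 = 0% (upper limit 2.82%) |
| 100 | 1/100 = 1.0% (0.03% to 5.45%) | 0/99 = 0% (upper limit 3.66%) |

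The rate hardly moves, but the event is gone from the table.

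**Direction**

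With x events among n dosed, leaving out one person who had the event gives (x − 1)/(n − 1), which is below x/n whenever x < n. Leaving out one person without it gives x/(n − 1), which is above x/n. Taking 13 events in 130 as an example (10.0%), the results are 12/129 = 9.3% and 13/129 = 10.1%. The direction therefore depends on whether those left out had events.

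**The case against.** The strongest reply is that *eligible* is used loosely and means no more than having passed screening. Section 4.1 says that eligible participants go on to the two sessions, Section 6.1 speaks of enrolling people who meet all criteria, and Section 10.1 makes randomization the last step of screening. On that usage, someone randomized and dosed in error counted as eligible at the time and stays in the set. This reading is reasonable and cannot be ruled out. But the word then has no function, and removing it costs nothing.

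Three further replies hold in part.

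- **Few people are likely to be affected.** Section 6.3 has the medical monitor assess unstable medical illness, and Section 8.4.3 repeats urine, intoxication and pain checks before each injection. Section 13 lists types of violation and does not predict how many will occur. Its PI decision concerns withdrawal of a subject, not removal of data from an analysis.
- **The events are not lost.** They are collected and, if serious, reported whatever the person's eligibility. The synopsis also has the medical monitor follow serious events throughout.
- **A fuller SAP is promised** in Section 14 and could change the definition. Nothing commits it to do so.

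A reader might go further and infer that the plan expressly removes these participants, or that it selects a low-risk set after exposure. The documents support neither. The exclusion is implied, no step for re-judging eligibility after dosing is described, and several entry criteria (speaking English, the age range, pain group) are not simply markers of naloxone risk.

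**Conclusion.** The point stands as a minor defect of definition. Followed literally, Section 14.1 leaves a dosed but ineligible participant out of the safety summaries, and no other section corrects this. The effect is confined to the tables and their denominators.

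It would be tempting to conclude that harm will be under-reported. That is possible, because several exclusion criteria are safety criteria, but it is not established: it requires that such participants occur, that the literal reading is applied, and that those left out have events at a higher rate than the rest.

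The size is about 0.8% to 1.0% of the denominator for each person left out, on the assumption that 100 to 130 are dosed. How many would be left out is unknown and probably small.

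**What to change.** In Section 14.1, delete *eligible* and define the Safety Population as all participants who receive at least one injection of study drug, naloxone or placebo, regardless of eligibility. State that safety data are summarised by the product received at each session, since each participant is due to receive both. In Section 14.4, name this set as the population for the adverse event tables. The promised SAP should carry the same definition.

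The cost is a sentence or two of text. Data collection, sample size, power, the primary analysis and the management of participants do not change.

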| SUBJECTS | group (PAIN) and 65 in the group without chronic pain (NO PAIN). Assuming a 25% drop-out rate, we expect to have 50 completers of both experimental sessions in each group. |

| SUBJECT | Inclusion Cuitario |
|-----------------|---|
| SUBJECT | Inclusion Criteria: |
| SELECTION | 1) Male and female adults aged 18-65 |
| CRITERIA | 2) Stable methodone dose (at least 21 days) verified by |
| | contacting participant's opioid treatment program |
| | 3) Understand and speak English |
| | 4) Urine toxicology screen negative for drugs of abuse and |
| | positive for methadone |
| | 5) Must be without by signs of intoxication as evidenced by |
| | ability to receive full dose of methadone prior to research |
| | activities |
| | 6) Presence of chronic pain (>3 months) for the PAIN group and |
| | absence of pain for the NO PAIN group. |
| | Exclusion Criteria: |
| | 7) Unstable psychiatric illness as assessed by the Mini |
| | International Neuropsychiatric Interview (e.g. active suicidal |
| | ideation, psychosis) |
| | 8) Unstable medical illness as assessed by the study's |
| | independent medical monitor (e.g. uncontrolled hypertension, |
| | recent myocardial infarction, recent stroke, unstable angina) |
| | that may be affected by precipitated withdrawal |
| | 9) Prescription opioid use besides methadone |
| | 10) Acute pain process unrelated to chronic pain |
| | 11) Women who are pregnant or lactating |
| | 12) Known allergy to naloxone |
| | Patients will be allowed to re-screen if it is expected that an inclusion |
| | criterion not met or an exclusion criterion met will change prior to the |
| | end of study recruitment. |
| TEST PRODUCT | · |
| TEST PRODUCT, | Naloxone 0.1 mg IM |
| DOSE, AND ROUTE | Product will be administered once at the beginning of a study session. |
| OF | Administration will occur two hours after methadone dosing. |
| ADMINISTRATION | |
| CONTROL | Placebo injection (0.9% Normal Saline) |
| PRODUCT, DOSE | Product will be administered once at the beginning of a study session. |
| AND ROUTE OF | Administration will occur two hours after methadone dosing. |
| ADMINISTRATION | |
| DURATION OF | Subjects will be on study for an average of two to four weeks |
| SUBJECT | Screening: 3 hours |
| PARTICIPATION | Sessions: Each session will last approximately four hours. |
| AND DURATION OF | Sessions must occur at least 48 hours apart. |
| STUDY | |

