| | The Group x Condition interaction will be examined to determine if | |
| | group differences vary by condition. Planned contrasts will explore | |
| | additive effects of chronic pain and withdrawal by examining whether | |
| | discounting by the PAIN group in the withdrawal condition is greater | |
| | than 1) discounting by the PAIN group in the control condition, or 2) | |
| | discounting by the NO PAIN group in the withdrawal condition. To | |
| | examine the effect of differing levels of peak aversive stimuli on | |
| | discounting, we will conduct analyses using only data from the | |
| | naloxone-precipitated withdrawal session that include peak COWS | |

Version #: 1.9 Version Date: 12/09/2020 Page 7 of 37

| | scores. |
|----------------------|---|
| Rationale for Number | Because there is no empirical data on within-subject changes in |
| of Subjects | discounting associated with naloxone precipitated withdrawal, we estimated change using data from a study by consortium PI [name] that used similar measures and found abstinence from smoking in nicotine-dependent individuals' decreased discounting rates ($f2$ =.02). For between group differences, we relied on data from our pilot study showing a correlation between pain and discounting (rho=.25) consistent with a small to medium effect size ($f2$ =.08). Three reported effect sizes for studies comparing opioid and tobacco dependent participants and non-dependent participants show much larger effects sizes (approximately $f2$ =0.4). Thus, basing the sample size on the effect size seen in the pilot study conservatively yields a sample size that will provide more than sufficient power to detect a group difference. Using these within-subject and between-subjects effect sizes, and assuming a correlation among repeated measures of 0.5, a final, analysis sample of 100 (50 per PAIN and NO PAIN groups) will provide greater than 80% power to detect significance (alpha=.05, 2-tailed) for between groups main effects, within-subject effects of condition, and the interaction between the two. |

Version #: 1.9 Version Date: 12/09/2020 Page 8 of 37

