6 SUBJECT SELECTION

6.1 Study Population

The participants will be adult persons (age 18-65) with opioid use disorder who are currently maintained on a stable methadone maintenance dose. Half (50) of the completers will have chronic pain (PAIN group) and half will be pain free (NO PAIN group). Otherwise, the participants will be healthy enough (as determined by medical history, physical, and EKG) for study entry. Participants will be required to abstain from illicit substances and alcohol throughout the trial.

It is estimated that approximately 200 persons will have an in-person screening to enroll 130 participants on methadone maintenance that meet all inclusion/exclusion criteria. We will need 100 completers to have the necessary power to perform our statistical analysis, 50 persons in the PAIN group and 50 persons in the NO PAIN group.

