14.2 Demographic and Baseline Characteristics

The PAIN and NO PAIN groups will be compared on all matching variables (methadone dose, cigarettes smoked per day, annual income, years of education, and age) using t-tests and chi-square tests as appropriate. If statistically significant differences are detected despite efforts to match during recruitment, matching variables will be included as covariates in subsequent analyses. It is recognized that this method is inferior to formal matching; therefore, substantial effort will be devoted to locating appropriately matched individuals. Measures obtained at 15-minute intervals during each session (pain, vital signs, opioid withdrawal, etc.) will be examined in terms of group comparability and to

Version #: 1.9 Version Date: 12/09/2020 Page 24 of 37

confirm that naloxone precipitated withdrawal symptoms compared to placebo. All psychometric, scaled measures will be scored according to standardized algorithms and internal consistency reliability examined. Given the design of the study, unit level missing data is not anticipated. Item level missing data will be minimized through supervised administration of measures. Missing data patterns will be examined and multiple imputation (SAS PROC MI) or other strategies employed as appropriate. Using methods developed by co-I [name], nonlinear regression will be used to calculate individual values of k, larger k values indicate greater discounting or more impulsiveness. K values are normalized using log transformation for parametric analysis (45).

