14.3 Analysis of Primary Endpoint

The primary hypotheses are that participants with chronic pain (PAIN) are more impulsive (larger k values) than participants without pain (NO PAIN) and that, within the same individual, k values will be larger in the naloxone-precipitated opioid withdrawal session compared to placebo. We will test these hypotheses using repeated measures analyses implemented in SAS PROC MIXED. The dependent variable is k (discounting). Independent variables include Group (PAIN vs. NO PAIN), a fixed, between-subjects effect and Condition (control vs. withdrawal), a repeated, within-subjects effect. The Group x Condition interaction will be examined to determine if group differences vary by condition. Planned contrasts will explore additive effects of chronic pain and withdrawal by examining whether discounting by the PAIN group in the withdrawal condition is greater than 1) discounting by the PAIN group in the control condition, or 2) discounting by the NO PAIN group in the withdrawal condition. To examine the effect of differing levels of peak aversive stimuli on discounting, we will conduct analyses using only data from the naloxone-precipitated withdrawal session that include peak COWS scores.

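### Cheap improvement: list Session (1 or 2) as a fixed effect in the section 14.3 primary model, because session order is what the trial randomises

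*Combined protocol and SAP*

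**What the plan says.** Section 4.1 describes two experimental sessions per participant, one with naloxone and one with placebo, in random order and at least 48 hours apart. PAIN and NO PAIN are not assigned at random, so session order is the only thing randomised.

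Section 14.3 specifies the primary model: "Independent variables include Group (PAIN vs. NO PAIN), a fixed, between-subjects effect and Condition (control vs. withdrawal), a repeated, within-subjects effect". It adds the Group x Condition interaction and planned contrasts, one of which compares the two conditions within PAIN. The synopsis repeats this model. Neither place lists a session, period or sequence term.

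The data set is reasonably clear. Section 14.1 says "Completer analysis will be the data collected for all of the completers (N=100 expected", and section 6.1 says "We will need 100 completers to have the necessary power to perform our statistical analysis". On losses, the synopsis says "Assuming a 25% drop-out rate, we expect to have 50 completers of both experimental sessions in each group" and section 12.2 says "Subjects who withdraw from the study will not be replaced". Section 14.6 has randomization in its title but states no method for balancing order, either overall or within the pain groups.

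**The concern.** Each participant performs the discounting task twice. Practice, familiarity with the setting or anticipation of the injection could make log k differ between the first and second visit for reasons unrelated to naloxone. In a model without Session, such a shift has two effects.

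- With balanced order it cancels from the Condition estimate but stays in the residual. The standard error is then too wide and power is lost.
- With unbalanced order among completers, part of the shift is counted as a naloxone effect.

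The Condition comparison is one of the two primary hypotheses, and its power at the planned size has no slack (see the working). A term that removes a possible nuisance at almost no cost is therefore worth listing.

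**Working it through.** **Inputs from the documents.** Two-sided alpha 0.05, correlation of repeated measures 0.5, within-subject f² = 0.02, analysis sample 100 (synopsis and section 14.6). Enrolment 130 with 25% drop-out, which gives 130 × 0.75 = 97.5, or about 98 completers.

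**Input assumed.** The session effect π, in SD units of log k, is given nowhere. I use 0 to 0.3.

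**1. The plan's own figure.** With m = 2 sessions, λ = f² × N × m / (1 − ρ) = 0.02 × 100 × 2 / 0.5 = 8.0. Noncentral F with 1 and 98 df gives 79.97% power for Condition. The stated power of more than 80% reproduces to rounding. At 97.5 completers λ = 7.8 and power is 79.0%.

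**2. Scale.** f = √0.02, so the Condition effect is δ = 2f = 0.283 SD. The SD of a within-person difference is √(2 × (1 − 0.5)) = 1.

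**3. Power when Session is left out, balanced order.** The naloxone-minus-placebo difference has mean δ − π if naloxone comes first and δ + π if placebo comes first. The estimate is unaffected, but the residual variance rises from 1 to 1 + π². Power is approximately Φ(√N × δ − 1.985 × √(1 + π²)), where 1.985 is the t critical value and √98 × 0.283 = 2.80.

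| π (SD) | Formula | Simulated, no Session | Simulated, with Session |
|---|---|---|---|
| 0 | Φ(2.80 − 1.985) = 0.79 | 0.792 | 0.792 |
| 0.1 | Φ(2.80 − 1.995) = 0.79 | 0.789 | 0.791 |
| 0.2 | Φ(2.80 − 2.024) = 0.78 | 0.780 | 0.792 |
| 0.3 | Φ(2.80 − 2.072) = 0.77 | 0.764 | 0.793 |

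The simulation used 200,000 runs with 98 completers. The loss is at most about 0.5 point at 0.1 SD and about 3 points at 0.3 SD.

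**4. Shift of the estimate when order is unbalanced.** Without Session the Condition estimate moves by π × (n₂ − n₁)/(n₁ + n₂), where n₁ and n₂ are completers with naloxone first and placebo first. With random 25% drop-out:

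- *Order fixed at 65/65.* The difference in completers has variance 2 × 65 × 0.75 × 0.25 = 24.4, so the ratio has SD 4.94/97.5 = 0.051. The 95th percentile of its absolute value is 0.10.
- *Coin-flip order.* SD is about 1/√97.5 = 0.10; 95th percentile 0.20.
- *Within PAIN, coin-flip order.* SD is about 1/√48.75 = 0.14; 95th percentile 0.28. With order fixed within PAIN it is 0.15.

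At π = 0.3 SD, the multipliers 0.10, 0.20 and 0.28 give shifts of up to 0.03, 0.06 and 0.08 SD, against a planned effect of 0.283 SD. At 0.1 SD they are a third of that.

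**The case against.** **Wording and timing.** The verb in 14.3 need not introduce a complete list of terms, and the opening of section 14 promises a detailed SAP. Both points are fair. They make this an unfinished specification and not an error, and the SAP is a natural place to finish it.

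**Size.** No passage reports a session effect. The largest value used, 0.3 SD, exceeds the treatment effect itself and still costs only about 3 points of power. Under random drop-out the shift averages zero over repeated trials. All of this stands. A reader might infer that the planned Condition estimate is biased or the sample size wrong; the documents support neither.

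**Session is not a remedy for drop-out.** It removes a session effect and nothing else. In one simulated case, loss between sessions depended on the naloxone-first response and was 38% in one order against 11% in the other. Adding Session there lowered the completer estimate from 0.217 to 0.202, against a true 0.283 (from 23% to 29% low). No passage links drop-out to k, so this is a caution about what the term can do.

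**A stronger reading about the data set.** A reader might infer that the efficacy set is undefined, or that "Given the design of the study, unit level missing data is not anticipated" contradicts the 25% drop-out. The documents do not support this. The synopsis gives "a final, analysis sample of 100 (50 per PAIN and NO PAIN groups", and sections 6.1 and 14.1 also point to people who finished both sessions. The sentence in 14.2 stands beside scale scoring and item-level missingness, so it can be read as being about whole instruments. It is followed by "Missing data patterns will be examined and multiple imputation (SAS PROC MI) or other strategies employed as appropriate". Nor is an all-available analysis plainly better. In the assumed scenarios, completers run 7–23% low when loss follows the naloxone-first response, and all-available data run 4–18% high when loss follows a stable trait after naloxone first only.

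**Conclusion.** The point holds as a low-cost improvement to the stated primary model. Session order is randomised, no Session term is listed, and nothing in the text assures balanced order among completers. The consequence is small to modest and depends wholly on an undocumented session effect. At 0.1 SD it is negligible. At 0.3 SD, power for Condition falls from 79% to 76%, and chance imbalance can move the estimate by 0.03 to 0.06 SD overall, or 0.08 SD for the within-PAIN contrast under coin-flip order. If there is no session effect, leaving Session out does no harm. These figures rest on f² = 0.02, a correlation of 0.5, about 98 completers and random drop-out.

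**What to change.** In section 14.3, and in the matching synopsis entry, list Session (1 or 2) as a fixed effect beside Group, Condition and Group x Condition. One term assumes that the shift is the same in both pain groups.

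The cost is one degree of freedom and no new data. With balanced order and 100 completers, power for Condition goes from 79.97% to 79.96%. With coin-flip order and no session effect the cost is about 0.4 point (0.791 to 0.787). As noted above, the term does not correct response-driven drop-out and can lower the completer estimate somewhat in that case.

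Optional, and separate from this point: keep completers as the primary set, as the documents imply, and fit the same model to all available sessions as a sensitivity analysis.
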